#### **Inclusion Criteria**

1. Informed consent provided electronically via the EDC, demonstrating that the subject understands the procedures required for the study and the purpose of the study
2. Male or female Subjects 18 years of age and up
3. Subjects must agree to practice at least one highly effective method of birth control for the duration of the study. This includes condoms with spermicide, oral birth control pills, contraceptive implants, intra-uterine devices, or diaphragms. Subjects not of reproductive potential will be exempt (e.g. post-menopausal, surgically sterilized)
4. Diagnosis of COVID-19 by at least one of the following:
  - a. Physician diagnosis based on clinical presentation
  - b. Positive RT-PCR analysis

#### **4. Prohibited Medications**

Found in Appendix 2

## **5. Subject privacy:**

Subjects will be assigned a unique eight-digit identification number. The first two digits will be the study identification number (44). The next three digits will be the specific test number and the last three digits will be a number sequentially assigned by the site via electronic data capture (EDC). This number will be used to identify the subject on all documents, study equipment, and test samples. Only personnel on the delegation log will have access to study documents. These documents will be stored in password-protected computers, and physical documents will be stored in secured research facilities per their SOPs.

## **6. Schedule of Events**

On next page

Assessment	Screening (Day -7 to Day 1)	Day 1	Day 2	Day 3	Day 4	Day 5	Day 6	Day 7	Day 8	Day 9	Day 10	Day 11	Day 12	Day 13	Day 14	Days 15-30	Month 1 (± 4 days)	Month 2 (± 4 days)	Month 3 (± 4 days)
Informed Consent & Demographics	X																		
Make list of prior and concomitant medications	X			X				X			X				X		X	X	X
Confirmation of COVID-19 diagnosis	X																		
Review of Medical Records	X																		
Prescription of Antimicrobials a	X																		
Provide home health equipment b	X																		
Pregnancy test c		X																	X
Call Subject at home d		X		X		X		X			X				X				
Vitals at home e		X	X	X	X	X	X	X	X	X	X								
Subject will complete AM/PM diary		X	X	X	X	X	X	X	X	X	X	X	X	X	X	X			
Hydroxychloroquine 200mg BID (or placebo)		X	X	X	X	X	X	X	X	X	X								
Azithromycin 500mg (2 tablets) once daily (or placebo)		X																	
Azithromycin 250mg (1 tablet) once daily (or placebo)			X	X	X	X													
Vitamin C 3000mg (2 capsules) twice a day		X	X	X	X	X	X	X	X	X	X								
Vitamin D 3000IU (2 capsules) twice a day		X	X	X	X	X	X	X	X	X	X								
Zinc 50mg (2 capsules) twice a day		X	X	X	X	X	X	X	X	X	X								
Vitamin C 1500mg (1 capsule) twice a day												X	X	X	X	X			
Vitamin D 1500IU (1 capsule) twice a day												X	X	X	X	X			
Zinc 25mg (1 capsule) twice a day												X	X	X	X	X			
Ask about AE and SAE				X				X			X				X		X	X	X
Vitals in-clinic f																	X	X	X
Physical exam																	X	X	X
EKG in-clinic																	X	X	X
Swabs for RT-PCR				X		X		X							X		X		X
Bloodwork g																	X	X	X
Review list of prior and concomitant medications		X	X	X	X	X	X	X	X	X	X	X	X	X	X	X	X	X	X
SARS-CoV-2 Antibody test (optional, +4 days)																	X		
Blood Hydroxychloroquine level (optional)																	X		

- a. To include hydroxychloroquine 200mg tablets (#20), azithromycin 250mg tablets (#6), vitamin C 750mg capsules (#80), vitamin D 750IU capsules (#80), zinc 12.5mg capsules (#80)
- b. To include EKG (worn continuously), pulse oximeter, and thermometer
- c. If Subject is a woman of childbearing potential
- d. To remind them to collect swabs for RT-PCT, ask about AE/SAE, ask about symptoms, and answer any questions
- e. To include EKG, oxygen saturation, and temperature
- f. Vitals in-clinic to include height (only at first visit), weight, blood pressure (following 5 minutes sitting) pulse, respiratory rate, temperature, and oxygen saturation (Optional)
- g. To include CBC, Complete Metabolic Panel, and CRP (details in section 9 Sample Collection) (Optional)

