## 3. Study Procedures:

- Diagnosis, Medical Review, and Prescription of Therapy (Screening, Day -3 to Day -1):
  - Subject will provide electronic informed consent via the EDC portal.
  - Medical Information
    - a. Study staff will review prior and concomitant medications, including over-the-counter medications and supplements.
    - b. Investigator will review the Subject's records during the screening process, looking at inclusion/exclusion criteria, gathering data on vital signs, EKG recordings, and oxygen saturation. These values will be used to compare to values obtained throughout the study. If any contraindication to participation is found, the study drugs will not be provided and the subject will be deemed a screen failure.
  - Diagnosis of COVID-19 will be confirmed
    - a. May be based on PCR testing results, rapid antigen testing results, or clinical presentation at screening as assessed by the Principal Investigator including symptoms such as:
      - Fever
      - Cough
      - Anosmia
  - Subject will be provided a daily diary for recording symptoms.
  - Subject will be randomized into Arm 1 or Arm 2
  - Prescription of treatment drugs
    - a. Arm 1: Medications will be prescribed for Quintuple Therapy
      - Hydroxychloroquine 200MG BID for 10 days, Azithromycin 500mg on day 1, 250mg day 2-5, Vitamin C 3000mg for 10 days, then 1500mg for 20 days, Vitamin D 3000IU for 10 days, then 1500IU for 20 days, and zinc 50mg for 10 days, then 25mg for 20 days.
    - b. Arm 2: Placebos and supplements will be provided (to ensure nutritional parity)
      - Placebo for Hydroxychloroquine BID for 10 days, Placebo for Azithromycin to be taken 2 the on Day 1, then 1 on Days 2-5, Vitamin C 3000mg for 10 days, then 1500mg for 20 days, Vitamin D 3000IU for 10 days, then 1500IU for 20 days, and zinc 50mg for 10 days, then 25mg for 20 days.
    - c. Drugs shall be taken first thing in the morning as soon as the patient has eaten. Vitamins will be taken with lunch and dinner, and then the evening dose of drugs will be right before bed.
  - Monitoring equipment provided
    - a. Home EKG recording device

- b. Pulse Oximeter
    - c. Thermometer
    - d. Urine Pregnancy test if applicable
  - Subject will be isolated as an outpatient
    - a. All CDC recommendations regarding self-quarantine must be followed
- Treatment Period
  - Day 1 following positive test (isolation)

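### Read per intake, the supplement labels in the Schedule of Events give twice the Section 3 dose and need twice the capsules dispensed

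*Combined protocol and SAP*

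**What the plan says.** The supplement regimen appears in four places in the protocol.

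- **Section 6, Schedule of Events.** Days 1-10: "Vitamin C 3000mg (2 capsules) twice a day", "Vitamin D 3000IU (2 capsules) twice a day" and "Zinc 50mg (2 capsules) twice a day". Days 11-30: "Vitamin C 1500mg (1 capsule) twice a day", "Vitamin D 1500IU (1 capsule) twice a day" and "Zinc 25mg (1 capsule) twice a day".
- **Section 6, footnote a.** The prescription is marked once, at screening, and includes "vitamin C 750mg capsules (#80), vitamin D 750IU capsules (#80), zinc 12.5mg capsules (#80").
- **Section 3, Study Procedures.** For both arms the regimen text gives "Vitamin C 3000mg for 10 days, then 1500mg for 20 days", vitamin D in the same numbers as IU, and zinc 50 mg then 25 mg over the same periods. The day tables split these into morning and evening amounts: 1500 + 1500 mg, 1500 + 1500 IU and 25 + 25 mg on Days 1-10, then 750 + 750 mg, 750 + 750 IU and 12.5 + 12.5 mg on Days 11-30.
- **Section 7, Dosage of Investigational Product.** Both arms are listed at 1500 mg, 1500 IU and 25 mg BID. No reduced phase is shown.

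**The concern.** Each supplement row of the schedule carries an amount, a capsule count and a frequency, and the three cannot all be right with the capsules dispensed. Two 750 mg capsules hold 1500 mg, not 3000 mg, and one holds 750 mg, not 1500 mg. Someone working from the amount and someone working from the capsule count would arrive at exposures that differ by a factor of two.

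The supplements are shipped to the home and self-administered by every subject in both arms. Section 1 says the later reduction is meant to limit side effects, and Section 13.1 lists serious risks for each supplement. Under the per-intake reading, the schedule's reduced phase equals the full Days 1-10 dose of Section 3, so the intended exposure in each phase is not clear from the protocol.

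**Working it through.** **Inputs.** Amounts, capsule counts and frequencies come from the six supplement rows of the Schedule of Events. Capsule strengths and quantities come from footnote a. The comparison regimen is the text and day tables of Section 3, and the BID figures of Section 7.

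**1. Reproduce the dispensed count.** From the schedule's capsule counts: 2 capsules × 2 per day × 10 days + 1 capsule × 2 per day × 20 days = 40 + 40 = 80. This matches footnote a for each supplement.

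**2. Check Section 3 against the supply.**
- Vitamin C: 3000 × 10 + 1500 × 20 = 60,000 mg; supply 80 × 750 = 60,000 mg.
- Vitamin D: 3000 × 10 + 1500 × 20 = 60,000 IU; supply 80 × 750 = 60,000 IU.
- Zinc: 50 × 10 + 25 × 20 = 1,000 mg; supply 80 × 12.5 = 1,000 mg.

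Section 3, the capsule counts and footnote a therefore agree exactly.

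**3. Establish the table's convention.** The azithromycin row for Day 1 gives 500 mg as 2 tablets once daily, and footnote a supplies 250 mg tablets: 2 × 250 = 500 mg in one intake. Over the course, 2 + 4 = 6 tablets, as dispensed. The hydroxychloroquine row gives 200 mg BID with 200 mg tablets: 2 × 10 = 20 tablets, as dispensed. In both rows the amount is per intake.

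**4. Apply that convention to the supplement rows.**

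| Supplement | Days 1-10: schedule | Days 1-10: Section 3 | Days 11-30: schedule | Days 11-30: Section 3 |
|---|---|---|---|---|
| Vitamin C (mg/day) | 3000 × 2 = 6000 | 3000 | 1500 × 2 = 3000 | 1500 |
| Vitamin D (IU/day) | 3000 × 2 = 6000 | 3000 | 1500 × 2 = 3000 | 1500 |
| Zinc (mg/day) | 50 × 2 = 100 | 50 | 25 × 2 = 50 | 25 |

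Every ratio is 2.0.

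**5. Compare with Section 7.** Vitamin C at 1500 mg BID is 3000 mg/day. On Days 1-10 the ratio is 6000 / 3000 = 2.0. Section 7 has no separate Days 11-30 figure, and its BID amounts are the same as the schedule's Days 11-30 labels (3000 / 3000 = 1.0). The same holds for vitamin D and zinc.

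**6. Compare the labels with the supply.**
- Vitamin C: 6000 × 10 + 3000 × 20 = 120,000 mg; 120,000 / 750 = 160 capsules, against 80.
- Vitamin D: 120,000 IU, also 160 capsules against 80.
- Zinc: 100 × 10 + 50 × 20 = 2,000 mg; 2,000 / 12.5 = 160 capsules, against 80.
- Time to exhaustion: 6000 / 750 = 8 capsules a day, and 80 / 8 = 10 days. Vitamin D (6000 / 750 = 8) and zinc (100 / 12.5 = 8) give the same result.

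**7. Try the alternative reading.** If the amounts are daily totals, vitamin C is 3000 / (2 × 2) = 750 mg per capsule on Days 1-10 and 1500 / (1 × 2) = 750 mg on Days 11-30, which is the dispensed strength. Zinc gives 50 / 4 = 12.5 mg and 25 / 2 = 12.5 mg. The course totals return to 60,000 mg, 60,000 IU and 1,000 mg, so the schedule, Section 3 and footnote a then agree.

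**The case against.** The strongest reply is that the schedule's amounts are simply daily totals carried over from the Section 3 regimen text, where the same numbers appear. Step 7 shows that this reading fits the capsule counts, the dispensed strength and quantity, and the day tables. It is a plausible account of how the rows arose. It does not clear them, because each row attaches the amount to a twice-daily frequency, nothing marks it as a daily total, and the two drug rows in the same table use the per-intake convention.

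A second reply is that a doubled dose is unlikely in practice. A subject would have to disregard the capsule count printed in the same row and take four capsules at each intake. Section 3 also gives daily morning and evening amounts, dosing is reviewed on the Day 1 video call, and the step-down is recalled on the Day 10 call. This stands, and it lowers the practical risk. A reader might infer that subjects would in fact receive twice the Section 3 dose; the documents do not support that.

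A reader might also infer that the schedule is double Section 7 throughout. It is not: the Days 11-30 labels equal Section 7's figures. Nor do the documents give any dose-related rate from which a difference in safety could be sized.

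Finally, Section 7 may be only a summary, since it gives no duration for hydroxychloroquine either. That is fair, but its silence on the step-down means that it cannot settle which phase the 1500 mg, 1500 IU and 25 mg BID figures belong to.

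**Conclusion.** The contradiction is real and lies in the amount labels of six schedule rows. Read per intake, they are exactly twice the Section 3 dose in both phases, twice the Section 7 dose on Days 1-10 only, and twice what footnote a can supply, with capsules running out after Day 10 of 30. The schedule's capsule counts already agree with Section 3 and with the supply.

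The size rests on two assumptions: that the supplement rows follow the per-intake convention of the drug rows, and that the quantities in footnote a cover the whole course, since the schedule shows one prescription and no resupply. If the labels are daily totals, the factor of two disappears and what remains is unclear wording, plus the missing reduced phase in Section 7.

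A reader might infer damage to the trial's comparison. The documents do not support that: the supplement instructions are identical in both arms, so the treatment contrast is not biased, and supplement dose does not enter the sample size. The point is still worth correcting, because these are dosing figures for subjects treating themselves at home.

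**What to change.** Reconcile the six supplement rows of the Schedule of Events with Section 3, Section 7 and footnote a. For each supplement and each phase, the amount per intake, capsules per intake, capsule strength, total count and Days 11-30 step-down should agree across all four places, and the schedule should say whether an amount is per intake or per day. Section 7 should show both phases or refer to the place that does. Which dose is intended is for the sponsor to state.

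The cost is amendment wording, with no new procedure. Any subject-facing dosing instructions derived from the schedule should be checked against the reconciled text.

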**Duration of Subject Participation (Study Visits)**

Subjects will be given the opportunity once diagnosis has been made via RT-PCR testing to participate. They may be recruited through the ProgenaBiome website, through a questionnaire. They may also be recruited through [www.clinicaltrials.gov](http://www.clinicaltrials.gov). Subjects may be referred by healthcare facilities. Subjects may also self-refer as well. All potential Subjects will be called during the recruitment process for screening assessments. The first step of this will be to obtain informed consent electronically, via the EDC. We will attempt to connect with these Subjects via Zoom/telemedicine. The validity of the test used to diagnose will be verified through medical records. (The diagnosis will be made by the Subject's evaluating physician or evaluation testing center, as part of the standard of care when infection is suspected). Following successful screening, Subjects will be randomized into the Arm 1 (treatment) or Arm 2 (placebo). At this time the associated treatment regimen will be prescribed and shipped to the Subject's home, along with home health equipment (MoMe Kardia II, thermometer, pulse oximeter and pregnancy test). Subjects will take azithromycin for 5 days, and hydroxychloroquine for 10 days, along with vitamin C, vitamin D, and zinc. Starting at Day 11 Subjects will discontinue hydroxychloroquine and reduce the doses of vitamin C, vitamin D, and zinc. The vitamin C, D, and zinc will be taken an additional 20 days at the reduced dose. Subjects will use the home EKG to transmit heart function information to the Study Team to be read by a board-certified cardiologist prior to dosing. The EKG will then be used daily for 10 days and results transmitted to the study team. Subjects will use a home pulse oximeter to monitor oxygen saturation and photographically report these values to the study team via the EDC. Subjects will track their symptoms using a daily diary (provided). Subjects will collect nasal or oropharyngeal swabs on Days 3, 5, 7, 14, and Month 1 and Month 3 for RT-PCR testing. Once Subjects have tested negative following treatment with HAZDpaC, Subjects will present to the clinic at 1, 2, and 3 months post-treatment for viral testing via RT-PCR. Alternatively, these visits may be conducted via videoconference and the subjects may collect these samples at home. At these visits blood will be drawn, a physical exam performed, and vital signs measured (optional). At the month 3 visit a pregnancy test will be given if applicable. Should Subject remain symptomatic at 2 weeks, or return to a positive state at any time during the trial they will be referred to their PCP by a phone call directly from the PI to the PCP. If at any time during the treatment phase or subsequent follow up Subject expresses and demonstrates a worsening or persistence of symptoms, they will be cared for according to standard of care or referred to their primary care provider, according to patient preference. The PI will discuss the case directly with that primary care provider. Subjects will continue to be followed for the remainder of the trial, and documentation of any additional treatments and Subject outcomes will be collected.

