## 2. Trial Objectives

Primary Study Objective	Study Endpoints
The rate of recovery of mild or moderate COVID-19 in Subjects using Quintuple Therapy	Number of Days Recovery from COVID-19 diagnosis to Recover via RT-PCR
Secondary Objectives	Study Endpoints
Assess the safety of Quintuple Therapy	Assess the symptom response to study therapy as measured by the survey in the EDC
	EKG response, oxygen saturation, and vital signs at baseline, 2 weeks, 1 month, and two months
Assess Tolerability of Quintuple Therapy	Assess Adverse Events and Serious Adverse Events due to Quintuple Therapy

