- Temperature

- d. Subject will take prescribed regimen

Drug	AM Dose	PM Dose
Hydroxychloroquine (or Placebo)	200mg	200mg
Vitamin C	1500mg	1500mg
Vitamin D	1500IU	1500IU
Zinc	25mg	25mg

- o Day 11-Day 13

- a. Subject will complete AM/PM diaries

- b. Subject will take prescribed regimen

Drug	AM Dose	PM Dose
Vitamin C	750mg	750mg
Vitamin D	750IU	750IU
Zinc	12.5mg	12.5mg

- o Day 14

- a. Subject will be called

- Remind them to collect nasal or oropharyngeal swab
- Ask about AE/SAE
- Symptom resolution or progression
- Answer any questions the Subject may have

- b. Subject will collect nasal or oropharyngeal swab

- c. Subject will complete AM/PM diaries

- d. Subject will take prescribed regimen

Drug	AM Dose	PM Dose
Vitamin C	750mg	750mg

Vitamin D	750IU	750IU
Zinc	12.5mg	12.5mg

- Day 15-30
  - a. Subject will complete AM/PM diaries
  - b. Subject will take prescribed regimen

Drug	AM Dose	PM Dose
Vitamin C	750mg	750mg
Vitamin D	750IU	750IU
Zinc	12.5mg	12.5mg

- Follow-Up Period (These visits can be conducted via videoconference or in person)
  - Month 1 (outpatient only AFTER negative test)
    - a. Vital signs (BP, HR, RR, oxygen saturation, temperature)
    - b. Assessment for AE and SAE
    - c. EKG (Optional)
    - d. Physical exam (Optional)
    - e. Blood draw for CBC/Complete metabolic panel/C-Reactive Protein/Blood hydroxychloroquine levels/SARS-CoV Antibody test (All optional)
      - Blood HQ levels will remain blinded from all but unblinded coordinator
    - f. Update list of prior and concomitant medications
    - g. Study team will collect nasal or oropharyngeal swab (If patient elects to refrain from this in-person visit they will collect this at home)
  - Month 2 (outpatient)
    - a. Vital signs (BP, HR, RR, oxygen saturation, temperature)
    - b. Assessment for AE and SAE
    - c. EKG (Optional)
    - d. Physical exam (Optional)
    - e. Blood draw for CBC/Complete metabolic panel/C-Reactive Protein (Optional)
    - f. Update list of prior and concomitant medications
  - Month 3 (outpatient)
    - a. Vital signs (BP, HR, RR, oxygen saturation, temperature)
    - b. Assessment for AE and SAE
    - c. EKG (Optional)
    - d. Physical exam (Optional)
    - e. Blood draw for CBC/Complete metabolic panel/C-Reactive Protein (Optional)
    - f. Update list of prior and concomitant medications

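### Month 1 and 2 vital signs and oxygen saturation form a secondary safety endpoint, but the Schedule and synopsis mark them optional while Section 3 does not, so the by-arm summaries may cover only a self-selected subset

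*Combined protocol and SAP*

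**What the plan says.** The synopsis objectives table and Section 2 (Trial Objectives) both give this secondary endpoint under the safety objective: "EKG response, oxygen saturation, and vital signs at baseline, 2 weeks, 1 month, and two months".

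Three places govern what is measured at the Month 1 to 3 visits:

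- Section 3, Follow-Up Period, lists "Vital signs (BP, HR, RR, oxygen saturation, temperature" at each visit with no optional tag. Other items in the same lists are tagged one by one, for example "Physical exam (Optional".
- Section 6, Schedule of Events, has an in-clinic vitals row at Months 1, 2 and 3. Its footnote f ends "respiratory rate, temperature, and oxygen saturation (Optional".
- The synopsis paragraph on duration of participation says: "At these visits blood will be drawn, a physical exam performed, and vital signs measured (optional".

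Section 3 introduces these visits with "Follow-Up Period (These visits can be conducted via videoconference or in person". Footnote b of the Schedule describes the home kit: "To include EKG (worn continuously), pulse oximeter, and thermometer".

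**The concern.** A named endpoint component should be collected from everyone at the named times. Here one part of the protocol reads as though it is, and two others let any subject decline.

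A subject decides whether to come to clinic, or to agree to be measured, after randomisation and after the treatment course. If that decision is related to how the subject feels, and differently so in the two arms, the by-arm summaries compare groups that randomisation did not form. Sections 15 and 16 say nothing about missing values. Section 15 defers further detail to an analysis plan due before database lock, but no analysis plan can recover readings that were never taken.

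**Working it through.** **Step 1. The plan's own figure.** The only computed figure is the sample size in Section 15: n = log(0.05) / log(0.995) = 597.647, rounded up to 600. It reproduces. It is used below only as a denominator, and the point does not depend on it.

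**Step 2. The passages side by side, Months 1 and 2.**

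| Item | Section 3 | Schedule | Synopsis visit paragraph |
|---|---|---|---|
| Vital signs, including oxygen saturation | no tag | optional (footnote f) | optional |
| EKG | optional | in-clinic row, no tag | not mentioned for these visits |
| Bloods | optional | optional (footnote g) | tag may extend to them |

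Two questions of scope arise. First, Section 3 never uses a word such as required. That status is inferred from the missing tag beside tagged neighbours. Second, the tag in footnote f could cover oxygen saturation alone. Footnote g ends in the same style, "To include CBC, Complete Metabolic Panel, and CRP (details in section 9 Sample Collection) (Optional", where it plainly covers the whole bloodwork row, so the whole-row reading is the more natural one. On the narrow reading, oxygen saturation is still optional in the Schedule and vital signs are still optional in the synopsis. Either way, each component is optional somewhere in current text.

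Month 3 has the same conflict but is not an endpoint time point.

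**Step 3. Is there another scheduled source?** The home vitals row of the Schedule is marked on Days 1 to 10 only. For Days 11 to 30, Section 3 lists diaries and supplements, plus a call and a swab on Day 14, and no readings. The Month 1 and 2 visits are therefore the only scheduled source for those time points. At a video visit, the kit could supply oxygen saturation and temperature if the subject still has it. It contains no blood-pressure device. The protocol does not say how vital signs are obtained by video.

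**Step 4. Illustration of size.** The documents give no uptake figure. With r the assumed proportion measured, the number observed is 600 × r and the standard error is multiplied by 1/√r.

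| r (assumed) | Observed | SE factor |
|---|---|---|
| 0.75 | 600 × 0.75 = 450 | 1/√0.75 = 1.15 |
| 0.50 | 600 × 0.50 = 300 | 1/√0.50 = 1.41 |
| 0.25 | 600 × 0.25 = 150 | 1/√0.25 = 2.00 |

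For bias, the full mean in one arm is r × (mean of measured) + (1 − r) × (mean of unmeasured). The observed mean is therefore off by (1 − r) × (mean of measured − mean of unmeasured), that is, by 0.25, 0.50 or 0.75 of that gap at the three uptake levels. The between-arm difference is distorted only if this product differs between arms. The documents give no basis for putting a value on the gap.

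**Step 5. The rest of the same endpoint.** It also names the EKG, which Section 3 marks optional at Months 1 and 2. It names 2 weeks as well, and neither Section 3 nor the Schedule has vital signs, oxygen saturation or an EKG on Day 14.

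**The case against.** The strongest reply is that the passages can be read together. The Schedule row concerns in-clinic vitals, the synopsis places its tag just after allowing video visits, and Section 3 lets a subject forgo attending in person. On that view only attendance is optional, and vital signs are taken in either mode. This is a fair reading, and it means the text shows ambiguity rather than a certain contradiction. It does not close the gap, because no procedure says how readings are taken by video and the kit cannot supply blood pressure.

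Other objections stand in part:

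- A reader might infer a loss of power for a safety comparison. The documents do not support that, because Section 16 plans no inferential analysis of safety parameters. The standard-error factors show only how much thinner the summaries could be.
- A reader might infer that different sites would follow different instructions. There is one study center. The conflict lies in what that one team is told.
- A reader might infer that Day 10 is the last possible home reading. It is the last scheduled one. The synopsis sentence on photographed oximeter readings gives no end date.
- That uptake would depend on symptoms or side effects is plausible, but the documents do not state it.
- The synopsis and the Month 1 heading tie follow-up visits to a negative test. Applied literally, that is a further post-randomisation selection, which removing the optional tag would not cure.

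**Conclusion.** The point holds as an unresolved inconsistency that can leave a named secondary safety endpoint measured in a self-selected subset at 1 and 2 months. The consequence is conditional: it arises only if the optional wording is followed and subjects decline. If Section 3 is followed, nothing is lost. The documents do not support the stronger inference that the endpoint will be missing or is already biased.

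The size is moderate at most. The endpoint is secondary and its analysis descriptive, so the harm is possible selection bias and fewer observations in by-arm summaries. The amount cannot be estimated from the documents, and the 450, 300 and 150 rest entirely on assumed uptake. The conclusion also rests on inferring from the missing tag that Section 3 requires the measurement. It is still worth correcting before follow-up begins, because a Month 1 or 2 reading not taken cannot be obtained later.

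**What to change.** Reconcile the synopsis visit paragraph, the Section 3 Follow-Up Period and Schedule footnote f so that:

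- Oxygen saturation and temperature are collected from every subject at Months 1 and 2. At video visits they are read from the supplied pulse oximeter and thermometer, with heart rate added if the device displays it, which the documents do not say.
- The text states whether every subject includes those who have not yet tested negative.
- Subjects keep these two devices until the Month 2 visit. The protocol is silent on return, so this must be written in.
- The blood-pressure and respiratory-rate part of the endpoint is limited to in-person visits, and the number measured is reported per arm at each time point.

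In the same edit, bring the endpoint into line with the EKG marked optional at Months 1 and 2 in Section 3, and with the 2-week time point that has no scheduled vital signs, oxygen saturation or EKG. Either schedule the home readings or remove those elements from the endpoint.

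The cost is wording in a few places and keeping an oximeter and thermometer with each subject until Month 2, which may delay re-use of the kits. Scheduling later home EKGs would extend that to the EKG device; removing the EKG from those time points would not.
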